2. STUDY OBJECTIVES

2.1 Primary Objective

This is a phase I/II prospective, randomized, multicenter, double-masked, vehicle-controlled clinical trial evaluating the safety and efficacy of corneal collagen cross-linking the keratoprosthesis carrier tissue in subjects who are candidates for high-risk keratoprosthesis implantation because of a history of corneal melts, sterile corneal ulcers, or autoimmune diseases (e.g., Stevens-Johnson syndrome, ocular cicatricial pemphigoid).

Objective 1:

Determine the safety of using a collagen cross-linked cornea as a carrier for the Boston Keratoprosthesis in subjects who are at high risk for corneal melts and are not candidates for a standard corneal transplant.

Objective 2:

Determine the efficacy of using a collagen cross-linked cornea as a carrier for the Boston Keratoprosthesis in preventing corneal melts and increasing the retention of the keratoprosthesis. This will be tested using the outcome measures listed in section 10.

2.2 Secondary Objective(s):

N/A

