6.8 Rescue Medication or Therapy

Subjects who do not retain the cross-linked KPro will be withdrawn from the study and the cornea will be replaced with a cadaver cornea or standard KPro at the physician's discretion.

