8.6 Follow-up Procedures

Additionally, to determine the safety and efficacy of using riboflavin-ultraviolet light induced collagen cross-linked cornea tissue in promoting retention, follow-up visits will be scheduled at Day 1 and 7 (± 3 days), week 4 (± 3 days), week 16 (± 2 weeks), week 24 (± 3 weeks), week 36 (± 3 weeks), and week 52 (± 4 weeks). Following week 52 visit, standard of care visits will occur every six months. The study will continue to collect data from these standard of care visits (post week 52 visit) in order to monitor subject safety for an additional 3 years or until study closure. Any procedures/exams performed during these visits will be standard of care and the MD will decide which procedures/exams are needed. Study staff will collect data for any procedures/exams that may be conducted as they pertain to the study (changes in medical history and medication prescription; BCVA, slit-lamp exam, IOP, funduscopy/B-Scan, OCT images, slit lamp photography and review of potential adverse events).

A description of imaging procedures follow in this section and a table of follow-up procedures organized by time-point can be found in section 7.7 below.

Cornea Thickness as measured by AS-OCT

Because corneal thinning will be used as a secondary endpoint and is an indication of corneal melts, cross- sections of the cornea will be obtained using anterior segment AS-OCT. This non-contact high-resolution imaging modality provides cross-sectional images of the cornea and anterior segment with a resolution of approximately 5-18 μ m. To evaluate the cornea, cross-sectional OCT images will be obtained at 0, 45, 90, 135, 180, 225, 270, 315 and 360 degrees.

Slit Lamp Photography

Because it is possible that slit lamp findings may be predictive of keratoprosthesis loss or corneal thinning, digital corneal photography will be done using a slit-lamp with a digital camera attachment and a flash-through-the-slit illumination system. By fine focusing on the surface of the cornea prior to corneal transplant surgery at the screening visit, and at Week(s) 1, 4, 16, 24, and 52, the photographer will capture the entire cornea using diffuse illumination and 10x magnification. If lids are drooping, the photographer will attempt to gently remove them from area of focus with a cotton swab.

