8.9 Schedule of Activities (Study Table)

	Screen	Day 0	Day 1	Wk. 1	Wk. 4	Wk. 16	Wk. 24	Wk. 36	Wk. 52
Visit Window	-60 days		+3 days	± 3 days	±3 days	± 2 weeks	± 3 weeks	± 3 weeks	± 4 weeks
Informed consent (study and surgical)	X								
Demographic data	X								
Medical/surgical history/chart review	X								
Review of Systems	X								
BCVA ***	X								
Slit-lamp exam***	X								
IOP ***	X								
Funduscopy/ Ultrasound B-scan (if necessary)***	X								
Contact Lens Review									
Pregnancy Test*	X								
Cornea thickness as measured by AS-OCT									
Slit Lamp Photography***	X								
Review Adverse Events									
Concomitant Medication Check	X								

Subjects will be instructed to strictly follow the study visit schedule.

* An additional urine pregnancy test needs to be performed just prior to surgery if there is greater than 30 days between screening visit and surgery.

**All subjects will be followed for at least 2 years. Following week 52 visit, standard of care visits will occur every 6 months for an additional 3 years or until study closure.

*** Historical results for best corrected VA, intraocular pressure, slit lamp examine, slit lamp photography and funduscopy can be used if completed within 60 days prior to screening visit

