10.3 Termination, of Subjects due to Adverse Events

Termination from the study will happen if any of the following occurs:

- Subject's wish to withdraw for any reason.

- Investigator or Research Monitor determination that it is not in the best interest of the subject to continue participation
- KPro removal

In the event an adverse event in the study eye is severe enough to require the donor study tissue to be removed and replaced with fresh cadaveric human cornea donor tissue with or without a keratoprosthesis, the patient will be terminated from further participation in the study. However, prior to termination the patient will be followed for 30 days after replacement surgery to collect any additional event data.

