11.6 Safety Analysis

Any adverse events, ocular or systemic, from all subjects will be utilized to summarize safety data for this study. The severity of each adverse event and the relationship of the event to the study medication will be assessed. If adverse events occur, the first concern will be the safety of the study participants. Any serious adverse event occurring during the study will be immediately reported to the principal investigator, and then to the PHRC, sub-sites, DOD, and FDA per the specified guidelines. The Research Monitor shall have the authority to stop the protocol, remove subjects from the protocol, and take any necessary steps to protect the safety and well-being of subjects until the IRB can assess the monitor's report. The monitor shall promptly report their observations and finding to the IRB or other designated official.

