#### Secondary Analysis

We plan to conduct a number of pre-specified analyses of secondary study endpoints. Analyses of secondary “time-to-event” type endpoints (time to retroprosthetic membrane treatment and time to

occurrence of vitritis) will use the Kaplan-Meier approach with log-rank test and Cox proportional hazards regression, similar to the primary analysis for time to device loss.

Comparison of cornea thickness metrics at week 1, 4, 16, 24, and 52 for treatment versus control group will be performed using the Mann-Whitney Wilcoxon test at each time point.

Furthermore, a mixed model regression analysis using generalized estimating equations (GEE) with compound symmetry covariance structure for repeated measures will be used to examine the effect of time, treatment and the interaction between them on cornea thickness to evaluate the change over time between and within the treatment groups. Comparison of twelve-month retention rate and incidence of delayed epithelial healing at Day 30 (week 4 visit) between groups will be performed using Chi-square test, or Fisher's exact test as appropriate.

In addition, the occurrence of any adverse events will be described and compared between treatment arms of the study.

We will run multivariable analysis with relevant information from the subject's ocular history to determine if certain characteristics inform or predict the loss of the study KPro or the survival time between insertion and removal. Among these, we will include age at study surgery, sex, race and whether patients- had previous KPros in the study eye and, if so, how many. For the subset of patients who did have previous Kpros in the study eye, we will look at the survival time of the one immediately before the study eye and compare it to the survival time of the study one. We will compare mean duration for these and analyze if there is a statistically significant difference among those who received a collagen cross-linked carrier cornea versus those who did not.

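### The general adverse-event comparison makes no allowance for time on study, although KPro removal ends follow-up, so it is biased if retention differs by arm

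*SAP*

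**What the plan says.** Safety is the first objective in Protocol 2.1: "Determine the safety of using a collagen cross-linked cornea as a carrier for the Boston Keratoprosthesis". For adverse events in general, the SAP (Secondary Analysis) says that "the occurrence of any adverse events will be described and compared between treatment arms of the study". Protocol 11.5 has the same sentence. Protocol 11.6 adds the population but no method: "Any adverse events, ocular or systemic, from all subjects will be utilized to summarize safety data for this study".

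The length of observation depends on the device:

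- **Device not retained.** Protocol 6.8: "Subjects who do not retain the cross-linked KPro will be withdrawn from the study". Protocol 10.3 lists KPro removal as a reason for termination, without limiting it to one arm. Where an adverse event leads to replacement, "prior to termination the patient will be followed for 30 days after replacement surgery to collect any additional event data".
- **Device retained.** Protocol 8.6 continues data collection after week 52 "in order to monitor subject safety for an additional 3 years or until study closure".
- **All subjects.** A footnote to the schedule in Protocol 8.9 states: "All subjects will be followed for at least 2 years".

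Some safety outcomes do handle time. The SAP lists three safety endpoints. Retroprosthetic membrane treatment and vitritis have Kaplan-Meier, log-rank and Cox analyses, and delayed epithelial healing is read at day 30. The adverse events of special interest in Protocol 9.1 (infectious keratitis, positive fungal rim culture, retinal detachment) are not among them and fall under the general comparison.

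**The concern.** The event that ends adverse-event observation is the one the treatment is meant to prevent. If cross-linking works, its arm is observed for longer. An adverse event with the same true rate in both arms would then be seen in more cross-linked eyes, because more eye-years are at risk. Events that themselves lead to removal concentrate in the arm that loses devices, so a count of any adverse event can move the other way. A crude comparison of occurrence therefore mixes safety with efficacy, in a direction that depends on the type of event. It is the only between-arm analysis planned for general adverse events and for the events of special interest.

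**Working it through.** **Inputs.** Twelve-month retention 0.55 against 0.85, alpha 0.05 two-sided, 80% power, 4% loss (Protocol 11.3). 68 eyes, mean follow-up 91 weeks, 20 removals, arms pooled (SAP, Preliminary Results). Event collection continues for d = 30 days = 0.082 years (Protocol 10.3).

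**Assumptions.** Time to removal is exponential, the 30 days run from removal, and the adverse-event rate r is constant and equal in both arms. The documents give no adverse-event rate, so I use r = 0.1, 0.3 and 1 per year.

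**The plan's own figure.** There is none for adverse events. The sample-size row for 0.55 against 0.85 confirms the removal model:

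- HR = ln 0.85 / ln 0.55 = 0.272.
- Freedman events = (1.960 + 0.842)² × (1.272/0.728)² = 23.9, so 24.
- Mean event probability = (0.45 + 0.15)/2 = 0.30, and 24/0.30/0.96 = 83.3, so 84 when rounded up to an even number. This matches the stated 84.
- The other two rows give 90 and 80, against 88 and 82 stated.

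**Removal rates per year (λ).**

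- Design: control −ln 0.55 = 0.598; cross-linked −ln 0.85 = 0.163.
- SAP pooled: 20 / (68 × 91 / 52.18) = 20/118.6 = 0.169, a 12-month retention of e^(−0.169) = 84%. I split this so that the two arms average 0.169. HR 0.5 gives 0.225 and 0.112; HR 0.272 gives 0.265 and 0.072.

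**Mean observation to the earlier of T and removal plus d:** M = d + (1 − e^(−λ(T−d)))/λ.

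For design control at T = 2: 0.082 + (1 − e^(−0.598 × 1.918))/0.598 = 0.082 + 1.141 = 1.22 years. For design cross-linked: 0.082 + 1.648 = 1.73 years.

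| Scenario | T (years) | Control | Cross-linked | Ratio |
|---|---|---|---|---|
| SAP pooled rate, HR 0.5 | 2 | 1.64 | 1.81 | 1.10 |
| SAP pooled rate, HR 0.272 | 2 | 1.59 | 1.87 | 1.18 |
| Design 0.55 v 0.85 | 1 | 0.79 | 0.93 | 1.19 |
| Design 0.55 v 0.85 | 2 | 1.22 | 1.73 | 1.41 |

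The other design rows give 1.44 (0.50 v 0.80) and 1.39 (0.60 v 0.90) at 2 years. Choosing the arm rates so that total removals over total eye-years equal 0.169 gives 1.19 in place of 1.18.

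**Share of eyes with at least one event by T:** F = 1 − e^(−rd) × [1 − r/(r+λ) × (1 − e^(−(r+λ)(T−d)))]. At T = 2, control v cross-linked:

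| r per year, equal in both arms | Pooled rate, HR 0.5 | Pooled rate, HR 0.272 | Design |
|---|---|---|---|
| 0.1 | 15% v 16% | 14% v 17% | 11% v 16% |
| 0.3 | 38% v 41% | 37% v 43% | 29% v 40% |
| 1 | 76% v 81% | 74% v 83% | 63% v 79% |

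There is no true difference in any cell. A rate per eye-year would give a ratio of 1.00 throughout.

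**When removal is itself recorded as an adverse event.** Let a share q of removals be recorded. The any-event share becomes F + qG, where G is the probability of removal by T with no other event observed: G = λ/(λ+r) × e^(−rd) × (1 − e^(−(λ+r)(T−d))) + e^(−rT) × (e^(−λ(T−d)) − e^(−λT)).

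At design retention, T = 2 and r = 0.3, G is 0.542 in control and 0.207 in cross-linked eyes. With q = 1 the shares are 83% v 60%, so the sign reverses. The arms break even at q = (0.397 − 0.292)/(0.542 − 0.207) = 31%. The break-even is 11% at r = 0.1 and 73% at r = 1.

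**The case against.** The best defence is that the plan is silent rather than wrong. It prescribes no crude test, and nothing in it bars rates or time to first event. That is correct. Still, occurrence compared between arms reads most naturally as a proportion, and silence leaves the choice until after the data are seen.

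Three further points stand:

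- **The gap is limited.** The named safety endpoints are time-to-event or fixed-time, so it would be wrong to infer that the whole safety evaluation is confounded.
- **The design rates overstate the likely size.** They imply an average 12-month retention of 70%, against about 84% from the SAP's pooled figures.
- **The trial is small.** With 34 eyes per arm (an equal split assumed), even 29% against 40% is about 10 against 13 or 14 eyes. The distortion affects how a safety table is read, not the primary conclusion.

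A reader might also infer that the cross-linked arm will look less safe. The documents do not support that. Protocol 8.8 and 10.3 describe study tissue being removed because of a severe adverse event in the study eye. If such events or the removals are counted, the any-event comparison can favour the arm that retains better. The SAP reports no removals by arm, so a real difference in exposure is not shown either.

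**Conclusion.** The concern holds as a conditional bias. If retention differs by arm, an unadjusted comparison of general adverse events, including those of special interest, is not interpretable as safety. Events unrelated to removal are over-represented in the arm that retains better, and events leading to removal work the other way.

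The SAP's own data suggest a modest 2-year exposure excess of about 10% to 18% for hazard ratios of 0.5 to 0.27. It would be about 41% at design retention and nil if retention is equal. These figures rest on exponential removal, equal constant adverse-event rates, the 30 days running from every removal, and use of the 91-week mean as eye-time at risk. The event percentages rest also on assumed rates. The change is worth making because safety is Objective 1 and the data needed are already collected.

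**What to change.** In the SAP:

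1. Report person-time by arm, and adverse-event rates per eye-year to the end of observation (including the 30 days after replacement surgery), with a rate ratio and 95% CI. Give weeks 0-52 and the time after week 52 separately.
2. For the adverse events of special interest, add time to first event with removal as a competing event, and say how events in the 30 days after removal are handled. Compare arms on the cause-specific hazard, and show the cumulative incidence of the event beside that of removal. Cumulative incidence alone carries the same exposure difference as the crude proportion.
3. State whether removal itself counts as an adverse event, and apply this in both arms.
4. Keep crude counts and percentages as description only.

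The sponsor should also reconcile the 2-year minimum follow-up for all subjects in Protocol 8.9 with termination at removal in Protocol 6.8 and 10.3.

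The cost is SAP wording and a few extra tables, with no new data. The rates assume a roughly constant hazard within each period. They also describe eyes while under observation, so after week 52 the eyes still at risk may differ between arms. The weeks 0-52 results should therefore carry more weight.

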## N = 68 subjects

**Preliminary Results:** Sixty-eight Kpros were implanted in 68 eyes (56 with previous sterile corneal ulceration) in 68 patients (15 with autoimmune disease) between 2017 - 2020 across 13 sites. The average age at the time of surgery was 62 [24-89] years, 42 (62%) subjects were male and 44 (65%) were white. The mean follow-up time was 91 weeks (SD= 47.6). A total of 20 KPros were removed with an average survival time of 70 [6-160] weeks.

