### Previous KPro

- Previous KPro in the study eye: yes/no
  - If yes, how many, how long were they in the eye for and why were they removed.
  - We don't have exact dates for all previous ones since some were done at other hospitals.

Reorganize the primary and secondary outcome measures into:

- Efficacy endpoints:
  - Removal or not of the study KPro
  - Rate of retention at 52 weeks
  - Time from KPro study surgery to ocular surgery done to address a melt, including partial graft

- Safety endpoints:
  - Incidence of delayed epithelial healing at day 30 (week 4 visit)
  - Time from surgery to retroprosthetic membrane treatment (laser or surgical interventions)
  - Time from surgery to occurrence of vitritis (sterile or infectious)

We will conduct an initial analysis to examine if distributions of baseline characteristics are balanced between the two treatment groups in our randomized study. Standard descriptive statistics will be reported, median (min-max) for numerical variables and frequency count (%) for categorical variables. Comparisons of numerical characteristics between treatment groups will be conducted using the Mann-Whitney U- test. Comparisons of categorical characteristics will be conducted using Chi-square, or Fisher's exact test as appropriate.

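### In eyes with a previous KPro, the SAP tests mean duration, which does not measure device life when most study KPros have no recorded removal and previous KPros enter only because they were removed

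*SAP*

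**What the plan says.** The SAP's Secondary Analysis ends with an analysis of eyes that had an earlier KPro. It will look at "the survival time of the one immediately before the study eye and compare it to the survival time of the study one". It continues: "We will compare mean duration for these and analyze if there is a statistically significant difference" between eyes given a cross-linked carrier and eyes that were not. It gives no test, pairing, time horizon or rule for devices not removed.

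Survival methods are specified elsewhere. The Primary Analysis applies Kaplan-Meier, log-rank and Cox to device loss in all randomized eyes. The Secondary Analysis says that time to membrane treatment and time to vitritis "will use the Kaplan-Meier approach with log-rank test and Cox proportional hazards regression, similar to the primary analysis for time to device loss". Neither statement covers the previous-KPro comparison, and Protocol 11.5 does not contain that analysis.

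On the earlier devices, the SAP's Previous KPro section asks "how long were they in the eye for and why were they removed", and says that the team does not "have exact dates for all previous ones since some were done at other hospitals". For the study devices, the opening summary of 68 subjects reports: "A total of 20 KPros were removed with an average survival time of 70 [6-160] weeks". It gives a mean follow-up of 91 weeks (SD 47.6).

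**The concern.** The two durations being compared are different kinds of quantity. A previous KPro has a finished duration, and it can be in the data only if it came out before study surgery. Long-lasting previous devices are therefore under-represented. Most study KPros, by contrast, probably have an unfinished duration that is cut off by the end of follow-up.

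A simple mean handles neither feature. Averaging time in place treats the end of follow-up as device loss. Averaging removed eyes only discards the eyes that did well. The previous-versus-study result could then show a difference when the two hazards are equal, and the between-arm result could miss a real benefit. A statement that cross-linked devices did or did not outlast the eye's previous device is easy to quote, so it should rest on a measure that can be interpreted.

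**Working it through.** The SAP gives no sample size, power or expected result for this analysis, so there is no planned figure to reproduce.

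**1. What a mean would be in the whole cohort.** Inputs from the SAP's opening summary: 68 eyes, 20 removals averaging 70 weeks, mean follow-up 91 weeks.

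- No recorded removal: 68 − 20 = 48, and 48/68 = 71%.
- Mean in removed eyes only: 70 weeks.
- Mean follow-up counted as duration: 91 weeks.
- Person-time estimate, constant hazard: 68 × 91 = 6,188 eye-weeks, and 6,188/20 = 309 weeks. Exact Poisson limits for 20 events are 12.2 and 30.9, giving 6,188/30.9 = 200 to 6,188/12.2 = 507 weeks.

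The last line takes the 91 weeks as covering all 68 eyes and ending at removal. Protocol 10.3 follows an eye for 30 days after replacement. Removing that time changes little: 20 × 30/7 = 86 weeks, and (6,188 − 86)/20 = 305.

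**2. Previous versus study KPro at equal hazard.** Suppose both devices have mean life m = 309 weeks, and that the previous implant date is uniform over a look-back of length L before study surgery. Given removal before study surgery, the density of its duration is proportional to exp(−t/m)(1 − t/L) on 0 to L. The expected previous mean is then about 48 weeks for L = 3 years and 131 weeks for L = 10 years. With study follow-up uniform on 30–180, 52–160 or 10–200 weeks, the study mean for time in place is 86 to 89 weeks. The study KPro looks longer-lived in the first case and shorter-lived in the second, with no true difference. The documents do not report the look-back, so these figures show only that the sign is undetermined.

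**3. Between arms.** Protocol 11.3 plans on 12-month retention of 0.50 vs 0.80, 0.55 vs 0.85 and 0.60 vs 0.90. With constant hazard, mean life = −52/ln(retention). With follow-up C under the same three assumed patterns:

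- mean time in place = average over C of m(1 − exp(−C/m));
- mean in removed eyes = average of [m − (C + m)exp(−C/m)], divided by average of [1 − exp(−C/m)].

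| Retention | True means (weeks) | True ratio | Ratio, time in place | Ratio, removed only |
|---|---|---|---|---|
| 0.50 vs 0.80 | 75 vs 233 | 3.1 | 1.52–1.57 | 1.25–1.35 |
| 0.55 vs 0.85 | 87 vs 320 | 3.7 | 1.50–1.55 | 1.23–1.32 |
| 0.60 vs 0.90 | 102 vs 494 | 4.8 | 1.47–1.53 | 1.21–1.30 |

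These pairs imply 39% to 55% removed, more than the 20/68 = 29% observed. Keeping the hazard ratios and lowering the hazard to 29% removed, the time-in-place ratio is 1.2 to 1.35.

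**4. Power.** This is a simulation at the hazard ratio for 0.55 vs 0.85 (0.272), with an assumed 10 eyes per arm and two-sided 0.05. At the hazard lowered to 29% removed, log-rank power is about 28% to 30%, and a t-test on time in place has about 13% to 18%. At the planning hazard the figures are about 43% to 48% and 25% to 35%.

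**The case against.** The SAP says survival time for both devices before it says mean duration, and it does not say that devices without removal are dropped or counted as failed. A restricted mean would fit the words. This has some force, but the operative sentence specifies a mean, the survival methods are assigned by name to other endpoints, and the opening summary already averages survival time for what appear to be removed devices only. The simple mean is the natural reading.

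The tested contrast may also be the within-eye change compared between arms. On that reading the selection of previous KPros happens before randomization and balances in expectation. That stands, but the unfinished study durations remain a problem.

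The modelled sizes are illustrations. The subset's size, share without removal and look-back are not reported. The constant-hazard model gives a removed-only mean of 53 to 60 weeks against the reported 70, so its fit is approximate.

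A reader might infer more than the documents support:

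- *That the test favours one arm.* It does not in expectation; the effect is dilution.
- *That the previous-versus-study comparison flatters the study KPro.* Step 2 shows that either sign is possible.
- *That 48 devices are known to be still in place, or that 71% applies to this subset.* The SAP supports only 48 eyes without a reported removal, in the whole cohort.

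**Conclusion.** The point holds as a minor one. A test of mean duration is the wrong method for these data, and no other section supplies a rule that repairs it. In the whole cohort the candidate means are 70 and 91 weeks, against about 309 weeks (200 to 507) when unfinished durations are allowed for. That last figure rests on constant hazard and on the 91 weeks covering all eyes.

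The previous-versus-study comparison is biased in an unknown direction. The between-arm comparison is attenuated and loses power, by an amount that depends on the assumed censoring patterns and hazards. That selection and censoring distort a simple mean does not depend on those assumptions.

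The analysis is best treated as exploratory. The primary log-rank and Cox analysis of device loss is not affected.

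**What to change.** Replace the mean-duration sentence in the SAP's Secondary Analysis with:

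> In eyes with a previous KPro, time from study surgery to device loss or replacement will be compared by arm with Kaplan-Meier curves, the log-rank test and a Cox model, censoring study KPros without removal at last follow-up. Duration of the previous KPro, where known, will be summarised descriptively by arm, with the number of unknown dates, and will not be tested against the study KPro duration. This analysis is exploratory.

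The preceding sentence, which announces the previous-versus-study comparison, should be aligned with this.

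The cost is a change of SAP wording, using methods the SAP already specifies on data already collected. The price is that there is no formal within-eye test. Precision will be low in a small subset under any method: in step 4 the log-rank test also usually misses the effect.
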